7.3 Discontinuation of Therapy and Withdrawal of the Patients from the Study

Study therapy should be discontinued and the patient should be withdrawn from the study due to any of the following reasons:

- Informed consent withdrawal (the patient has made the decision to stop the participation in study for any reason)
- The patients require other antibiotic treatment
- Development of any adverse event, including serious adverse event, clinical significant deviation in the laboratory results, or concomitant disease, which at the investigator's opinion indicates, that continuation of the study medication administration is not at the patient's best interest
- Pregnancy
- Termination of the study by the Sponsor (e.g. in case of poor safety results)
- Termination of the study by the Regulatory Authority (e.g. in case of poor safety results).

CONFIDENTIAL Page 36 of 88

In all cases the reason of termination of participation in study must be recorded in eCRF. When the patient is withdrawn from the study, all efforts should be made to perform all procedures scheduled for the "early termination visit":

- if the "early termination visit" coincides in time with scheduled visit the procedures of that visit should be done (Section 9.2);
- if the "early termination visit" coincides in time with unscheduled visit the minimum number of procedures should comply with the "End of treatment visit" (Section 9.2.3).

All the patients withdrawn from the study will receive treatment in accordance with the standards adopted in the hospital.

Withdrawn patients will not be replaced.

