8.7.2 Prohibited and limited in use therapy

During treatment period (from Visit 1 to Visit 3) the following medications should be prohibited:

- 1. Antacids, multivitamins containing calcium, magnesium, iron, zinc, or aluminum, and sucralfate should be prohibited within 3 hours before and after oral administration of the investigational drug. Intravenous therapy should not be coadministered with any solution containing multivalent cations, e.g., magnesium, through the same intravenous line.
- 2. Probenecid.

During study period (from Visit 1 to Visit 5) the following medications should be prohibited:

- 1. Drugs that may prolong the QT interval with known risk or possible risk of Torsades de Pointes (TdP). The list of these drugs is presented in Appendix 3.
- 2. Chemotherapeutic agents or antitumor drugs.
- 3. Other systemic antibacterial drugs (except for treatment failure).
- 4. Systemic immunosuppressive drugs, including inhaled steroids.
- 5. Drugs that may act to alter the signs and symptoms of infections (e.g., antipyretics, analgesics, antihistamines, or cough suppressants) since day 3 (including) of the treatment.
- 6. Investigational products other than studied in this trial and other than the patient has been randomized.

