- Assessment of vital signs 2 hours \pm 30 minutes after oral dose administration
- Documentation of adverse events
- Compliance check
- Assessment of concomitant medication and therapies.

9.2.3 Visit 3 (end of treatment visit, within 1-2 days after the last dose)

Visit 3 will be performed within 1-2 days after the last dose, but not less than 24 hours after the last dose of the study drug. The Visit can be performed at outpatient department. The following measures will be performed during the Visit 3 in accordance with the study schedule of assessments:

- Physical examination
- Assessment of vital signs
- ECG (before or 30 minutes after blood samples collection)
- Haematology test

CONFIDENTIAL Page 50 of 88

- Biochemical assay
- Urinalysis
- Pulse oximetry
- Collection of a sputum sample for culture (if the patient has sputum)
- Collection of a blood sample for culture (sampling should not be conducted in case of negative culture at Visit 1)
- Clinical response assessment
- Documentation of AEs/SAEs
- Assessment of concomitant medication and therapies

All the procedures should be performed within one day.

9.2.4 Visit 4 (test of cure visit, within 7-9 days after the last dose)

Visit 4 will be performed within 7-9 days after the last dose. The Visit can be performed at outpatient department. The following measures will be performed during the visit in accordance with the study schedule of assessments:

- Physical examination
- Assessment of vital signs
- ECG (before or 30 minutes after blood samples collection)
- Haematology test
- Biochemical assay
- Urinalysis
- Chest X ray (two-dimensional roentgenogram) or chest computed tomography
- Pulse oximetry
- Collection of a sputum sample for culture (if the patient has sputum)
- Collection of a blood sample for culture (sampling should not be conducted in case of negative culture at Visit 1)
- Clinical response assessment
- Documentation of AEs/SAEs occurred since the last visit
- Assessment of concomitant medication and therapies (since the last visit)

All the procedures should be performed within one day.

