12.6.3 Secondary efficacy analyses

As a supportive analysis, the primary efficacy endpoint will be analyzed in the CE population using the same method as that used for the primary efficacy analysis.

For secondary efficacy analyses, the clinical success rates of the patients in the mITT and CE populations at Visit 2 (switch to oral therapy) and Visit 3 as well as the number (proportion) of patients who needed other antibiotic treatment (treatment failure) will be analyzed using a two-sided 95% confidence interval (equality test) calculated based on the same statistical test as for the primary analysis.

Additionally, the results of statistical comparison of the clinical success rates using the logistic regression will also be provided.

Time to switch therapy from i.v. to oral therapy will be evaluated using the Kaplan – Meier survival analysis method and compared by log-rank test between treatment groups. The Kaplan-Meier curves will be presented graphically.

Microbiological efficacy endpoints will include microbiological success rates evaluated per each patient and by identified pathogens in b-mITT and BE.

The percentage and the number of patients with microbiological success and failure will be summarized by visit and treatment group. Microbiological success is defined as the assessments of eradication and presumed eradication. Other results of assessments (excluding unevaluable) will be regarded as microbiological failure. The difference between microbiological success rates and its CI will be calculated using the same method as that used for the secondary efficacy endpoints.

The percentage and number of the baseline-identified strains (sputum and blood culture) with microbiological success and failure will be summarized by visit and treatment group. The frequency of each category and sample source (sputum and blood culture) will be presented separately and by treatment group. Microbiological data by identified pathogens will be analyzed descriptively.

Microbiological efficacy evaluation

Based on the results of culture (bacteriological) study the microbiological response will be assessed. Microbiological response is defined as:

- 1. Eradication (admission pathogen[s] is absent),
- 2. Presumed eradication (if no material available for culture because of clinical success)
- 3. Persistence (admission pathogen[s] is present),
- 4. Presumed persistence (no material available for culture for patients with clinical failure),

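### A negative culture taken after a replacement antibiotic has started can be scored as eradication, so a rescued clinical failure can count as a microbiological success (secondary endpoint, mainly b-mITT)

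*Combined protocol and SAP*

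**What the plan says.** Section 7.3 lists as a reason for stopping study therapy and withdrawing: "The patients require other antibiotic treatment". On withdrawal, "all efforts should be made to perform all procedures scheduled for the 'early termination visit". If that visit is unscheduled, "the minimum number of procedures should comply with the 'End of treatment visit"; if it coincides with a scheduled visit, that visit's procedures apply. Sections 9.2.3 and 9.2.4 include sputum culture (if there is sputum) and blood culture (unless the Visit 1 culture was negative) at Visits 3 and 4. Section 7.3 then states: "All the patients withdrawn from the study will receive treatment in accordance with the standards adopted in the hospital".

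Section 8.7.2 prohibits, through Visit 5, "Other systemic antibacterial drugs (except for treatment failure"), so an antibiotic given for treatment failure is not itself prohibited medication. Table 10-1 makes the need for additional antimicrobial therapy a clinical failure.

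Section 12.6.3 defines the microbiological categories. Two matter here: "Eradication (admission pathogen[s] is absent") and "Presumed persistence (no material available for culture for patients with clinical failure"). Eradication and presumed eradication together are microbiological success; everything else except unevaluable is failure. The categories set no condition on non-study antibacterials.

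**The concern.** The microbiological score is meant to say what the study drug did to the pathogen. Once a replacement antibiotic has been given, a negative culture no longer answers that question, yet the definition still credits the study drug. For a rescued patient the score then depends on whether and when a sample was taken.

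Microbiological efficacy is a stated secondary objective (Section 4.2), and Section 12.6.3 plans a between-arm difference with a confidence interval. Moving rescued failures into the success column raises the rate in each arm and can hide an excess of rescue in one of them.

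**Working it through.** The plan gives no microbiological success rate, margin or b-mITT size, so there is no figure to reproduce. The check is a trace of the rules, followed by a formula with assumed inputs.

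**1. Is there a culture, and when?** Sections 7.3 and 9.2.3 bring cultures into the withdrawal visit. Section 10.2.3 ties the baseline sample to before the start of therapy and the Visit 2 sample to before the first oral dose. Visits 3 and 4 are timed only from the last study dose. Nothing ties any sample to the first dose of a non-study drug.

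**2. How is a rescued patient scored?**

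| Rescued patient | Table 10-1 | Section 12.6.3 |
|---|---|---|
| Pathogen present | Clinical failure | Persistence: failure |
| Nothing to culture | Clinical failure | Presumed persistence: failure |
| Sampled after the new antibiotic, pathogen absent | Clinical failure | Eradication: **success** |

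**3. Which population?** Section 12.2 keeps patients with violations and deviations in b-mITT. It removes from CE and BE those with less than 7 days of study drug (violation) and those who skip the test-of-cure visit (major deviation). What remains in BE is the patient with at least 7 days of study drug who is rescued later and whose withdrawal visit coincides with Visit 4.

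**4. Size within an arm.** Let r be the proportion of b-mITT patients rescued and q the proportion of those with a negative culture taken after rescue started. Compared with scoring these patients as failures:

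inflation = r × q

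Neither r nor q is in the documents. Assumed ranges give:

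| r | q = 0.5 | q = 1.0 |
|---|---|---|
| 5% | 2.5 points | 5 points |
| 10% | 5 points | 10 points |
| 15% | 7.5 points | 15 points |

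In patients: Section 12.10 expects 171 × 0.8 = 136.8, about 137 per arm in mITT. If 20–50% of these have a baseline isolate (assumed), b-mITT has 137 × 0.2 = 27.4 to 137 × 0.5 = 68.5 per arm. The misclassified number then runs from 27.4 × 0.05 × 0.5 = 0.7 to 68.5 × 0.15 × 1.0 = 10.3 per arm.

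**5. Effect on the difference** (N = nemonoxacin, T = Tavanic):

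scored difference = true difference + (r_N q_N − r_T q_T)

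With a common q, and rescue as the only cause of failure, the true difference is −(r_N − r_T) and the scored difference is (1 − q) times that. For r_N = 15% and r_T = 5%, the true difference is −10 points, scored as −5 (q = 0.5), −2 (q = 0.8) or 0 (q = 1).

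With unequal q the direction is not fixed. For r = 10% in both arms, q_N = 1.0 and q_T = 0.5, the shift is 10 − 5 = +5 points where the true difference is zero.

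**The case against.** The strongest reply concerns sequence. Section 9.3 describes the early termination visit as the visit at which withdrawal is decided, which puts the sample at or around the stop of study drug and often before the first replacement dose. Section 7.3 also mentions the visit before it mentions hospital-standard treatment. This stands: sampling after rescue is possible, not shown to be usual. It is not an ordering rule, however, and the definition gives the wrong answer whenever the order is reversed.

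A reader might infer from Section 9.2.3, "but not less than 24 hours after the last dose of the study drug", that rescue will normally be running by then. The documents do not support this. That minimum belongs to scheduled Visit 3, and Section 7.3 imports that visit's procedures, not its timing.

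A reader might also take the 18% assumed not to reach clinical success (100 − 82, Section 12.10) as the amount at stake in each arm. It is not. It would require every clinical failure to be rescued, sampled and negative, whereas Table 10-1 also counts persistent signs, unchanged imaging and death from pneumonia. Sputum is taken only if present and judged necessary and possible (Section 10.2.3), and blood only if positive at Visit 1.

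Three further limits stand:

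- No section assigns an early termination culture to a visit, so the visit-specific effect is unknown.
- The endpoint is secondary and has no non-inferiority margin.
- Section 12.5 leaves missing and spurious data to a separate SAP whose text is not supplied. A valid culture taken under rescue is neither missing nor evidently spurious, so that deferral does not clearly cover it.

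**Conclusion.** The point holds as a defect in a stated scoring rule: followed as written, it can turn a rescued clinical failure into a microbiological success. It concerns the secondary microbiological endpoint, mainly in b-mITT, with a small residue in BE. It should not be read as affecting both populations alike, or as touching the primary analysis, where additional antimicrobial therapy is already failure.

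The size is r × q per arm and cannot be computed from the documents; 2.5–15 points corresponds to the assumed 5–15% rescued and 50–100% negative. The pull toward zero rests on a similar q in both arms and on the arm with lower true success having more rescue. The change is worth making before the SAP is finalized, which Section 12.9 places ahead of database close-out.

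**What to change.** In Section 12.6.3 or the SAP:

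- A culture taken after the first dose of a non-study systemic antibacterial given for CAP treatment failure is not used to score eradication. From then on the patient is a microbiological failure.
- Extend the definition of presumed persistence to cover this case; at present it requires that no material be available.
- Keep a same-day culture if source records show that it preceded the first dose; otherwise treat it as taken after rescue.
- Add a sensitivity analysis scoring these patients as unevaluable.
- State the visit to which an early termination culture is assigned.

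Section 8.7 already records start dates of concomitant drugs in the eCRF. It lists dates, not times, and does not clearly reach drugs begun after withdrawal. Confirm that the replacement antibiotic's start date is entered, and use source records for same-day order.

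The cost is a few sentences and a derived flag. The downside is that some patients whose pathogen was truly cleared by study drug will be scored conservatively as failures; the sensitivity analysis shows how much that matters. Patient care and sample size do not change.

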8 TREATMENT

8.1 Treatments Administered

Two investigation products, two comparators and 2 placebos will be used during the study. All the investigational medicinal products will be blinded (please refer to Section 8.6).

In this trial the investigational products are Nemonoxacin 500 mg (250 ml), solution for infusion, and Nemonoxacin 250 mg, capsules.

Nemonoxacin 500 mg (250 ml), solution for infusion, will be administered daily as single intravenous infusion over 90-110 minutes followed by infusion of Placebo (100 ml), solution for infusion, over a minimum duration of 60 minutes to maintain the blinding. Daily dose of Nemonoxacin will be 500 mg (250 ml). Intravenous therapy will be given for at least 3 days and may be prolonged by a decision of investigator up to 7 days. The possibility of further prolongation of intravenous treatment (for more than 7 days) has to be discussed with the study Medical Adviser. The decision about switching to oral therapy should be based on assessment of patient's condition using the criteria of clinical stability.

After the switch to oral therapy on Day 4(8) of the study the patients who receive intravenous therapy with Nemonoxacin, solution for infusion, will receive therapy with Nemonoxacin, capsules. Please note that the first dose of oral drug will be administered on the same day when the "switch" is performed (e.g. the patient will receive the first dose of oral drug on Day 4 if the "switch" is performed at Day 4, etc.).

Nemonoxacin 250 mg, capsules, will be administered at a dose of 500 mg once daily (two 250 mg capsules). The duration of oral therapy will be judged by investigator and oral therapy will last until and including Day 7(14) of the study.

Tavanic[®] 500 mg (100 ml), solution for infusion, and Tavanic[®] 250 mg, over-encapsulated for the blinding purpose film coated tablets, will be used as the comparators in this study.

Tavanic[®] 500 mg (100 ml), solution for infusion, will be administered daily as single intravenous infusion over a minimum duration of 60 minutes. Daily dose will be 500 mg (100 ml). To maintain double-blinding before the infusion patients in this group will receive Placebo (250 ml), solution for infusion, over 90-110 minutes. Intravenous

CONFIDENTIAL Page 37 of 88

therapy will be given for at least 3 days and may be prolonged by a decision of investigator up to 7 days. Further prolongation of intravenous treatment (for more than 7 days) has to be discussed with the study Medical Adviser. The decision about switching to oral therapy should be based on assessment of patient's condition using the criteria of clinical stability.

After the switch to oral therapy on Day 4(8) of the study the patients who receive intravenous therapy with Tavanic[®], solution for infusion, will receive therapy with Tavanic[®], over-encapsulated film coated tablets. Please note that the first dose of oral drug will be administered on the same day when the "switch" is performed (e.g. the patient will receive the first dose of oral drug on Day 4 if the "switch" is performed at Day 4, etc.).

Tavanic[®] 250 mg, over-encapsulated film coated tablets, will be administered at a dose of 500 mg once daily (two capsules each containing 250 mg film coated tablet). The duration of oral therapy will be judged by investigator and oral therapy will last until and including Day 7(14) of the study.

8.2 Investigational Medicinal Products (IMPs)

Table 8-1 Investigational Medicinal Products (IMPs)

Investigational	Nemonoxacin
product 1:	
INN:	Nemonoxacin
Chemical name:	7-[(3S,5S)-3-Amino-5-methyl-peperidin-1-yl]-1-cyclopropyl-8-
	methoxy-4-oxo-1,4-dihydro-quinoline-3-carboxylic acid
Pharmaceutical form:	Solution for infusion
Strength:	500 mg (250 ml)
Rout of	Intravenous
administration:	
Supplier:	R-Pharm JSC (Russia)
Manufacturer:	Zhejiang Medicine Co. (China)
Investigational	Nemonoxacin
product 2:	
INN:	Nemonoxacin
Chemical name:	7-[(3S,5S)-3-Amino-5-methyl-peperidin-1-yl]-1-cyclopropyl-8-
	methoxy-4-oxo-1,4-dihydro-quinoline-3-carboxylic acid
Pharmaceutical form:	Capsules
Strength:	250 mg
Rout of	Orally
administration:	
Supplier:	R-Pharm JSC (Russia)
Manufacturer:	Lotus Pharmaceutical Co., Ltd. (Taiwan)
Comparator 1:	Tavanic [®]
INN:	Levofloxacin
Chemical name:	(-)-(S)-9-fluoro-2,3-dihydro-3-methyl-10-(4-methyl-1-piperazinyl)-7-
	oxo-7H-pyrido[1,2,3-de]-1,4-benzoxazine-6-carboxylic acid
	hemihydrate
Pharmaceutical form:	Solution for infusion

CONFIDENTIAL Page 38 of 88

Strength:	500 mg (100 ml)
Rout of	Intravenous
administration:	
Supplier:	R-Pharm JSC (Russia)
Manufacturer:	Sanofi-Aventis Deutschland GmbH, Germany (Germany)
Comparator 2:	Tavanic [®]
INN:	Levofloxacin
Chemical name:	(-)-(S)-9-fluoro-2,3-dihydro-3-methyl-10-(4-methyl-1-piperazinyl)-7-
	oxo-7H-pyrido[1,2,3-de]-1,4-benzoxazine-6-carboxylic acid
	hemihydrate
Pharmaceutical form:	Film coated tablets (each tablet is placed into a capsule shell (over-
	encapsulated) for blinding purposes)
Strength:	250 mg
Route of	Orally
administration:	
Supplier:	R-Pharm JSC (Russia)
Manufacturer:	Tablets manufactured by Sanofi Winthrop Industrie, France (France),
	are over-encapsulated into capsule shells by Lotus Pharmaceutical Co.
	Ltd. (Taiwan)

There will be two placebo formulations used during the study:

- Placebo (250 ml) 0.9% NaCl (250 ml), solution for infusion
- Placebo (100 ml) 0.9% NaCl (100 ml), solution for infusion

All placebo formulations will be supplied by the Sponsor. Placebo (250 ml), solution for infusion, is manufactured by Zhejiang Medicine Co. (China). Placebo (100 ml), solution for infusion, is manufactured by Dalchempharm OJSC (Russia).

8.3 Non-Investigational Medicinal Products

There will be no Non-Investigational Medicinal Products (NIMP) in this study.

8.4 Packaging, labeling and storage of IMPs

Nemonoxacin 500 mg (250 ml), solution for infusion, and Placebo (250 ml), solution for infusion, will be supplied in the flexible bags. Tavanic $^{\$}$ 500 mg (100 ml) solution for infusion, and Placebo (100 ml), solution for infusion, will be supplied in the glass bottles.

Nemonoxacin 250 mg capsules and Tavanic® 250 mg over-encapsulated film coated tablets will be supplied in the plastic bottles.

Each unit of container will be appropriately labeled in accordance with local regulations. The label will clearly indicate "only for clinical study". The label will be affixed to the primary container (bottles/flexible bags).

All IMPs will be stored at room temperature (less than or equal to 25°C) under secure conditions and protected from light. The temperature in the storage room should be controlled on a regular basis and should be documented in the Temperature Log.

At the site the IMPs should be stored in a locked room. Only unblinded staff appointed by Principal Investigator (PI) will have an access to the room. Unblinded staff will be instructed on the proper storage conditions of IMPs, return of drug and package.

CONFIDENTIAL Page 39 of 88

All containers of the IMPs, both used and unused, must be saved for a monitoring by unblinded CRA and possible audit by an assigned Sponsor's designee.

8.5 Method of Assigning Patients to Treatment Groups

At Visit 1 (Day 1) to minimize or avoid bias randomization will be done. The study will utilize IWRS for randomization of the eligible patients. In accordance with randomization number each patient will be assigned to one of two treatment groups at the ratio of 1:1 (see Table 6-1):

- Investigational drug (Nemonoxacin) group
- Comparator (Tavanic®) group.

8.6 Blinding

This study has a double-blind and double-dummy design with 2 placebo formulations (see Section 8.2) needed for maintaining the blinding of intravenous treatment.

Intravenous drug dispensing procedure

Only the unblinded staff appointed by PI at each investigational site and an unblinded CRA will be aware of the intravenous treatment received by the patient. Neither the patients nor any of the principal investigators (PI)/ co-investigators/ other clinical staff (blinded staff), involved in the treatment of the patients, Sponsor and CRO (except an aforementioned unblinded CRA) will be aware of the intravenous treatment received by the patient.

The unblinded staff will include person, appointed by PI from study site staff (e.g. a doctor, a nurse, a pharmacist) at each investigational site. These unblinded person will be responsible for the supply of the drugs intravenous treatment for the certain patient.

After enrollment and obtainment of the subject study number using the interactive web response system (IWRS) each eligible patient will be randomized. The PI or one of the unblinded persons appointed by PI will access the IWRS at Visit 1 and IWRS will randomize the patient and provide the medication identification number of the investigational drug to be dispensed. For details refer to the IWRS manual, please.

Once the unblinded person receives the number, he/she will prepare the supply.

Unblinded person will take the appropriate solutions according to the medication identification number.

Nemonoxacin 500 mg (250 ml)/Placebo (250 ml), solutions

The flexible bag with Nemonoxacin/Placebo (250 ml) solution will be packed in an opaque bag that will be sealed by a sticker to prevent breaking the code. Then, the opaque bag with flexible bag inside will be put into the special designed empty packing box with number "1" on the label. The label with randomization number will be stuck to the box. After that the unblinded person will insert a spike of infusion set into the administration port of the flexible bag with Nemonoxacin /Placebo (250 ml) solution and will prime the infusion set.

CONFIDENTIAL Page 40 of 88

Tavanic® 500 mg (100 ml)/Placebo (100 ml), solutions

The unblinded person will peel off the outer aluminum band from the top of the glass bottle with Tavanic Placebo (100 ml) solution. The bottle will be packed in a carton with a hole on the bottom for the administration port of the bottle. The carton will be sealed by a sticker to avoid breaking the code. Then, the carton with glass bottle inside will be put into the special designed empty packing box with number "2" on the label. The label with randomization number will be stuck to the box. After that the unblinded person will insert a spike of infusion set into the administration port of the bottle with Tavanic Placebo (100 ml) solution and will prime the infusion set.

Then, a person from blinded staff will take the supply, dose the patient, and return the supply after the dosing to the unblinded staff.

Oral drug dispensing procedure

Neither the patients nor any of the principal investigators (PI)/ co-investigators/ other clinical staff (blinded staff), involved in the treatment of the patients, Sponsor and CRO will be aware of the oral treatment received by the patient.

Since Day 4(8) of the study (switch from i.v. to oral therapy) the patients will receive the blinded capsules of oral drugs according to the medication identification number. Each patient will receive daily treatment with 2 capsules containing either Nemonoxacin (Nemonoxacin 250 mg capsules) or Levofloxacin (Tavanic[®] 250 mg, film coated tablets).

The randomization number will only be broken for an individual patient in an emergency such as an SAE that requires knowledge of which IMP was taken so that the SAE can be treated appropriately. In the event of SAE, if possible, the investigator should contact the medical adviser before the investigational drug blind will be broken to discuss the need for unblinding. If the randomization number for a patient is broken, the investigator must withdraw the patient from the study.

